Wage supplements to increase employment. Our research shows that participants will not attend our training program or work consistently on training without incentives ([name] et al., 1996; Wong et al., 2004a,b; Koffarnus, Wong et al., 2013; Koffarnus, DeFulio et al., 2013). To increase motivation of participants to engage in IPS and obtain employment, participants will earn wage supplements for maintaining competitive employment. Wage supplements can promote employment in welfare recipients (Berlin, 2007; Michalopoulos, 2005; Riccio et al., 2010). Given the failure of employment interventions for unemployed drug users, combining IPS and wage supplements is warranted and could increase employment in this difficult population.

Abstinence contingency in provision of wage supplements to prevent relapse. Our research shows that employment alone is not sufficient to maintain abstinence. In the most relevant study (DeFulio et al., 2009), after completing Phase 1, participants who initiated cocaine abstinence were hired in our Phase 2 data entry business for one year and randomly assigned to two groups. Employment Only participants could work independent of their urinalysis results, like typical employment; Abstinence-Contingent Employment participants had to provide drug-free urine samples to work and maintain maximum pay. During Phase 2, Abstinence-Contingent Employment participants provided significantly more cocaine-negative samples than Employment Only participants (79.3% and 50.7%, respectively). Based on this study, we expect that many participants who become employed will relapse to cocaine use when employment-based abstinence reinforcement is discontinued. To sustain abstinence, participants who become employed will earn abstinence-contingent wage supplements as long as they continue to provide drug-free urine samples. If a participant obtains competitive employment, the participant will receive wage supplements (\$8/hr) for verified employment. The maximum amount in wage supplements will be available as long as the participant continues to provide drug-free urine samples. To reduce the burden of providing urine samples, the probability of being required to provide urine samples will be gradually reduced over time, as we did previously (DeFulio et al., 2009).

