Review and expungement of criminal record. Criminal records are a major barrier to competitive employment in adults with a history of illicit drug use. To help participants prepare for competitive employment, we may collaborate with community partners (e.g., Maryland Legal Aid) who offer free legal assistance to participants in Phases 1 and 2. This assistance typically consists of determining eligibility for expungement, processing petitions for expungement of criminal records, and other free services approved by the legal team. Participants are notified by research staff that legal assistance is available, and that participation is voluntary. We may collect data to describe and evaluate the expungement process so we may better understand legal barriers to employment in adults with a history of illicit drug use. The data we would collect are the types of offenses participants have on their public records (i.e., records available to potential future employers), the number of convictions on record, which records are eligible or ineligible for expungement, whether petitions for expungement are filed by the legal team, whether petitions for expungement are granted or require a hearing, and how long it takes for participants to have their records expunged. We may publish an article to describe the expungement process and de-identified data of our participants. All data that we collect and publish on the criminal histories of our participants will be data that are publicly available.

Random Assignment

Participants (N = 120) will be randomly assigned to an IPS Only (Control) or IPS Plus Abstinence-Contingent Wage Supplements group. A computerized urn randomization procedure (Wei & Lachin, 1988) will be used to balance groups on three baseline characteristics that may influence outcome: (1) percentage of the three monthly urine samples collected prior to random assignment that are positive for cocaine (\geq rolling median, Y/N); (2) percentage of the three monthly urine samples collected prior to random assignment that are positive for opiates (\geq rolling median, Y/N); and (3) completed high school or obtained a GED (Yes/No). Participants will be stratified by cocaine and opiate use because drug use at random assignment should predict abstinence from opiates and cocaine and possibly employment during the intervention evaluation period. High school completion or GED should be associated with employment

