during the intervention evaluation period. This number of stratification variables has been sufficient to balance groups in past studies.

Individual Placement and Support (IPS) & Abstinence-Contingent Wage Supplement Group

This study will evaluate a novel intervention designed to promote long term employment and drug abstinence. The intervention will combine Individual Placement and Support with abstinence-contingent wage supplements. This group will receive the full intervention being evaluated in this study for one year.

Individual Placement and Support (IPS). To increase employment, after completing Phase 1 of the Therapeutic Workplace, participants will be offered Individual Placement and Support (IPS) model of supported employment for one year. IPS involves rapid job search, promotes competitive employment, considers the participant's preferences, and provides job supports and benefits counseling. The employment specialist will establish relationships with potential employers and work with participants to identify potential jobs, prepare applications, and to apply for positions. The employment specialist will provide IPS under the supervision of [name] (Co-I), the developer of IPS, and [name] (Consultant).

Fidelity measures will be collected to ensure that IPS is followed consistently. Using the procedures outlined by Bond, Peterson, Becker and [name] (2012), two trained IPS assessors will visit our research unit for 1.5 days per year and use IPS-25 to assess IPS fidelity. IPS-25 consists of 25 items that specify critical features of IPS. Each item is rated on a 5-point scale which represents the degree to which the program adheres to that feature of IPS. The assessors will interview our staff and our employment specialist, observe team meetings and community contacts with employers, interview clients, and review client charts. After the site visit, the assessors will independently make fidelity ratings and then reconcile discrepancies. The assessors will also prepare a fidelity report and provide recommendations for improvement. IPS-25 fidelity scores have been shown to be significantly associated with rates of employment (Bond et al., 2012). This fidelity assessment process has led to programs attaining good fidelity across hundreds of implementations.

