The primary outcome measures will be analyzed with a longitudinal logistic regression model using GEE (Diggle et al., 2002). We used Liu and Liang (1997) to determine the total N required to detect differences between groups with 80% power. The adjacent figure shows the total number of participants (N) that would be required to detect a difference of 15% between the IPS Only and the IPS Plus Abstinent-Contingent Wage Supplement with the 12 monthly assessments. The adjacent figure shows possible percentages for the IPS Only group because that value affects the sample size required. Fifteen percent is smaller than any difference in any Therapeutic Workplace study in which we promoted cocaine abstinence in methadone patients. This difference is also smaller than any difference between Control and IPS groups in the percentage of participants that become employed. Based on this, we need a maximum of 120 participants (horizontal dashed line) to detect a difference between the IPS Only and the IPS Plus Abstinent-Contingent Wage Supplement groups of 15% or more on each primary outcome.

Statistical Analyses

Main analysis. All measures assessed repeatedly over time will be analyzed with a longitudinal logistic regression model. Within-person correlated outcomes will be handled using generalized estimating equations (GEE; Zeger et al., 1988). Measures assessed once will be analyzed using logistic regression. The magnitude of effect for both logistic regression and GEE will be expressed using odds ratios with 95% CI. Analyses will include all randomized participants as intent-to-treat, and will be adjusted for pre-specified covariates used for stratification (Pocock et al., 2002). Tests will be two-sided and p-values <.05 will be considered significant.

Moderator analyses. We will conduct analyses to identify variables that moderate the outcomes of our two primary outcome measures, employment and drug (opiates and cocaine) abstinence. We will examine differences in efficacy as a function of two variables assessed prior to random assignment by including interaction terms in our regression models: 1) Percentage of urine samples negative for opiates and cocaine at the three monthly urine samples collected prior to random assignment. 2) Completed high

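### The rolling-median cut for the drug-use strata collapses for a drug whenever more than half of participants so far are negative on all three pre-randomisation samples

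*Combined protocol and SAP*

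**What the plan says.** Section 4, Random Assignment: "A computerized urn randomization procedure (Wei & Lachin, 1988) will be used to balance groups on three baseline characteristics that may influence outcome". The first is the "percentage of the three monthly urine samples collected prior to random assignment that are positive for cocaine (\geq rolling median, Y/N". The second is the same measure for samples "that are positive for opiates (\geq rolling median, Y/N". The third is "completed high school or obtained a GED (Yes/No". The reason given for the two drug-use factors is prognostic: "Participants will be stratified by cocaine and opiate use because drug use at random assignment should predict abstinence from opiates and cocaine", and possibly employment. The section adds: "This number of stratification variables has been sufficient to balance groups in past studies".

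Section 7.c, Main analysis, says the models "will be adjusted for pre-specified covariates used for stratification". It does not say whether the drug-use covariates enter as the Y/N codes or as percentages.

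The plan gives no rule for ties or for a median of 0%, does not say how a missed sample counts, and does not say whether the participant being allocated contributes to the median.

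**The concern.** Three samples allow only four values: 0, 33, 67 or 100% positive. No percentage is below 0, so at a rolling median of 0% the test is passed by everyone. A participant with no positive sample and one with three then enter the urn as the same type.

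Drug use before randomisation is stratified because the plan expects it to predict the primary outcomes. When the cut collapses, the trial has one or two fewer working strata than it states. If the GEE also adjusts for the Y/N code, that covariate is constant or nearly so and cannot correct a chance imbalance. Both protections would then be lost together. The assurance about past studies concerns the number of stratification variables, not where this cut falls.

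**Working it through.** The plan gives no stratum sizes, rolling median or Phase 1 positive rates, so there is no figure to reproduce. N = 120 is used below only as the trial size.

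**1. When the median is 0%.** More than half of participants must be 0 of 3 positive for that drug. With independent samples and per-sample positive rate p, this needs (1 − p)³ > 0.5, so p < 1 − 0.5^(1/3) = 0.206. With within-person correlation (beta-binomial, assumed) of 0.2, 0.4, 0.6 and 0.8, the threshold rises to 25%, 30%, 36% and 43%.

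**2. What the schedule implies.** Assessments fall every 30 days in Phase 1 (Section 4, Intake, Outcome & Economic Assessments), and pay is independent of urinalysis for the first 5 weeks, or 35 days (Section 4, Phase 1). So the first sample, at about day 30, precedes the contingency and the other two follow it. This is approximate, because Section 4 also says the start of the requirement will be varied.

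The first sample caps the result: P(0 of 3) cannot exceed the share negative on it. As an illustration, take the later two samples as 79.3% negative. Section 3 reports this for an earlier study's contingent arm, which "provided significantly more cocaine-negative samples than Employment Only participants (79.3% and 50.7%, respectively". The lower end of each range below assumes independence; the upper end is latent correlation 0.95.

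- First sample 30% positive: 0.70 × 0.793² = 0.44, rising to 0.68. A zero median is likely at moderate correlation.
- First sample 49.3% positive (the complement of 50.7%): 0.507 × 0.793² = 0.32, rising to 0.51. The median is usually above 0.
- First sample 80% positive: 0.20 × 0.793² = 0.13, and at most 0.20. The median stays above 0.

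**3. Effect on balance.** Single-factor urn (one ball per arm at the start, one added to the opposite arm after each assignment), N = 120, latent-normal samples. Urn parameters, positive rates and correlations are all assumptions. The SD is that of the between-arm difference in percent positive, in points. Paired entries are latent correlation 0.5 / 0.7. With 700 runs, the simulation error of an SD near 5 is about 5/√1400 = 0.13.

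| Positive rate, samples 1, 2, 3 | Coded 'Y' | SD, written rule | SD, simple randomisation | SD, any-positive cut |
|---|---|---|---|---|
| 20, 15, 15% | 97 / 98% | 5.0 / 5.4 | 4.8 / 5.2 | 3.5 / 3.8 |
| 30, 20.7, 20.7% | 85 / 93% | 5.2 / 6.1 | 5.5 / 6.5 | 4.0 / 4.3 |
| 49.3, 20.7, 20.7% | 63 / 66% | 4.9 / 5.4 | – | 4.4 / 4.5 |

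At high use (80, 50, 50%; latent correlation 0.3–0.7) the order reverses. The written rule codes 62–65% 'Y' with SD 4.2–4.8. The any-positive cut codes 83–91% 'Y' with SD 5.1–5.6.

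**4. The drugs fail separately.** With opiates 15% and cocaine 50% positive per sample (within-person correlation 0.5, 1,500 runs), the written rule codes 99.4% 'Y' for opiates. The SD of the between-arm difference in the share with any opiate-positive sample is 7.8 points, as under simple randomisation, and the chance of a gap above 10 points is 0.20 under both. A cut at 0 against 1 or more positives gives 5.3 points and 0.06. In the same runs the cocaine factor still balances: SD 6.7 points against 8.6 under simple randomisation.

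**The case against.** The strongest reply is that a zero median may never occur. The 79.3% comes from participants who had already become abstinent and were then held under a contingency. Here, everyone who reports for assessment at the end of Phase 1 is randomised (Section 4.a), and the abstract describes people still using cocaine during opioid agonist treatment. Applying 79.3% to all three samples would also ignore the day-30 sample. This stands. For cocaine, if about half or more are positive at day 30, the cut mostly works. For opiates the documents give no rate at all. What keeps the failure plausible is that Section 5 requires no cocaine-positive or illicit-opiate-positive sample: a methadone- or buprenorphine-positive urine is enough.

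A reader might infer that the urn stops balancing drug use exactly when Phase 1 succeeds. The documents do not support that. Phase 1 can succeed while the median stays at 33% or more, because the pre-contingency sample counts. The median can also be zero with no Phase 1 effect, given the entry criteria. One drug can collapse while the other still balances, and participants allocated before the median reaches 0% are split normally.

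A reader might also infer bias. Allocation stays random, so there is none. Nor can it be said that the model adjusts for nothing: Section 7.c leaves the coding open, and adjusting for the percentage would deal with a chance imbalance.

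Finally, the COVID-19 procedures in Section 4 speak of completing remaining assessments, so allocation may be over. That limits what a change to the urn can achieve, but not a change to the covariate.

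**Conclusion.** The point holds in a conditional form. That the written rule puts every new participant in one stratum at a median of 0% is exact and needs no assumption, and the plan has no fallback. Whether the median reaches 0% cannot be settled from the documents.

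Where it does, with assumed positive rates of 15–30% per sample and latent correlation 0.5–0.7, the SD of the between-arm difference in percent positive is about 5–6 points. That is about the same as simple randomisation; a working cut gives about 3.5–4.3. These figures also rest on assumed urn parameters, which the plan does not state. The consequence is lost balance and precision on a factor the plan itself calls prognostic. No effect on power or on either primary outcome has been quantified. The change is cheap and worth making.

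**What to change.** In Section 4, Random Assignment, keep the rule of at or above the rolling median, and add, separately for cocaine and opiates: when the rolling median is 0%, code 'Y' only if the percentage is above the median, that is, if any of the three samples is positive. This costs one line in the urn program and one in the protocol. In simulation it matched or beat the written rule, to within simulation error, in every scenario tried. Do not use a fixed any-positive cut throughout, because it balances worse when use is high. Do not switch to strictly above the median at all times, because that moves the collapse to a median of 100%.

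In Section 7.c, state that the primary GEE models adjust for the percentage of the three samples positive for each drug, not the Y/N code. The urn already needs these percentages, so no new data are required, and this protects the comparison even if allocation is complete. In that case, also report the realised Y/N split for each drug.

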Resetting the wage supplement value. Participants will continue to be eligible to earn the maximum in abstinence-contingent wage supplement as long as they continue to provide opiate- and cocaine-negative urine samples on all required sample collection days. If a participant ever fails to provide a scheduled sample or provides a urine sample that is positive for opiates or cocaine, the value of the wage supplement will be reduced to \$1.00 per hour and the frequency of required urine collections will be increased to the initial frequency of two days per week on average. The value of the wage supplement will

be increased by \$1.00 per hour for every day that the participants provide a drug negative sample. In addition, the probability of required urine sample collections will be gradually decreased again as long as the participant continues to provide drug-negative urine samples on required urine collection days. By the end of the year, participants should be required to provide urine samples on one randomly selected Monday, Wednesday or Friday every two weeks.

Individual Placement and Support (IPS) Only Group

Participants assigned to the Individual Placement and Support (IPS) Only group will receive the IPS intervention as described above. This group will receive IPS as it has been implemented thus far for people with severe mental illness. Participants in this group will not receive the monetary incentive for performing IPS tasks or maintaining competitive employment (wage supplement).

Intake, Outcome & Economic Assessments

For the primary aim of the study, assessments will be conducted at intake, every 30 days throughout the 3-month abstinence initiation period, every 30 days throughout the 12-month intervention evaluation period after random assignment and then at 3, 6, 9 and 12 months after the end of the intervention evaluation period. Assessments will be administered using Qualtrics, a web-based software (<http://qualtrics.com/>) to administer and record responses for the questionnaires administered that we are using in our other protocols. If the Qualtrics is not available, we may administer assessments using paper forms. The paper versions of the assessments are included in the section 19 for Supplemental Study Documents. Urine samples will be collected at each of these time points and we may test for cocaine, opiates, marijuana, amphetamines, methamphetamines, methadone, buprenorphine, barbiturates, benzodiazepines, MDMA, PCP, and oxycodone.

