Specific Aim. Assess the effectiveness of the *IPS* Plus Abstinence-Contingent Wage Supplements in promoting employment. We will assess rate that participants report being employed at the 12 monthly assessments during the year after random assignment (Y/N at each assessment).

b. Secondary outcome variables.

Specific Aim. Assess the effectiveness of the *IPS* Plus Abstinence-Contingent Wage Supplements in reducing injection drug use. We will assess the rate that participants report injecting drugs in the past 30 days at the 12 monthly assessments in the year after random assignment (Y/N at each assessment).

Specific Aim. Assess the effectiveness of the *IPS* Plus Abstinence-Contingent Wage Supplements in reducing drug-related HIV risk behaviors. We will assess the rate that participants report sharing injection equipment (needles/syringes without disinfecting, cookers/cottons/rinse water, or drug solution) or trading unprotected sex for drugs or money in the past 30 days at the 12 monthly assessment during the year after random assignment (Y/N at each assessment). If the *IPS* Plus Abstinence-Contingent Wage Supplements reduces cocaine and opiate use, it should reduce these risk behaviors.

Specific Aim. Assess the effectiveness of the *IPS* Plus Abstinence-Contingent Wage Supplements in reducing family poverty. We will assess whether family income is at or below the federal poverty level at the 12 monthly assessments during the year after random assignment (Y/N at each assessment) with and without wage supplement earnings. *IPS* Plus Abstinence-Contingent Wage Supplements should reduce poverty.

Specific Aim. Assess the effectiveness of the *IPS* Plus Abstinence-Contingent Wage Supplements in promoting long-term drug abstinence and employment and in reducing HIV risk. We will compare the groups on all measures of heroin and cocaine use, employment, and HIV risk behaviors at 3-, 6-, 9- and 12-month follow-up assessment time points after *IPS* and abstinence-contingent wage supplements have ended.

Specific Aim. *Assess the costs of treatment for IPS Only and IPS Plus Abstinence-Contingent Wage Supplements.* We will assess the total cost per participant of both study interventions. We expect that treatment costs for IPS Plus Abstinence-Contingent Wage Supplements will be higher per person relative to the IPS Only due to the wage supplements and because we expect that IPS Plus Abstinence-Wage Supplement participants will have greater treatment engagement.

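### The models for injecting and HIV risk behaviour (and, less importantly, poverty) omit each outcome's own pre-randomisation value, giving up precision that should be cheap to recover

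*Combined protocol and SAP*

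**What the plan says.** Section 7.b words three secondary aims as reductions: in injecting, in drug-related HIV risk behaviour (sharing equipment, or trading unprotected sex) and in family poverty. Each outcome is a yes/no rate at the monthly assessments after randomisation. For injecting: "We will assess the rate that participants report injecting drugs in the past 30 days at the 12 monthly assessments".

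Under Main analysis in 7.c, every repeated measure goes into a longitudinal logistic GEE model, and the analyses "will be adjusted for pre-specified covariates used for stratification". The Random Assignment part of section 4 lists those covariates: cocaine and opiate results on the three monthly urines before randomisation, each split at a rolling median, and high school or GED completion. Pre-randomisation injecting, risk behaviour and poverty are neither stratifiers nor covariates. The moderator analyses in 7.c concern employment and drug use only.

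Earlier measurements appear to exist. Section 4 (Intake, Outcome & Economic Assessments) says "assessments will be conducted at intake, every 30 days throughout the 3-month abstinence initiation period". Section 4.a calls the Phase 1 monthly visits outcome assessments and randomises those who attend for assessment when Phase 1 ends. Section 10 lists an assessment immediately before random assignment. Section 5 requires unemployment at entry, but neither current injecting nor an income ceiling.

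**The concern.** A person's own recent status is usually the best available predictor of a repeated yes/no behaviour. The plan already acts on this for abstinence, where the urine strata are the baseline counterpart of the outcome, and for employment, where only unemployed people enrol. The three outcomes above have no such counterpart. Because injecting is not an entry criterion, the trial can enrol both current injectors and people who do not inject.

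Two things are at stake. First, precision: N = 120 was set for the primary outcomes, so the secondary ones have no guaranteed power to spare. Second, interpretation: if one arm happens to start with fewer injectors, part of that difference will appear in the reported odds ratio, and a decision to adjust made after seeing it would be data-driven.

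**Working it through.** **1. The plan's own figure.** Inputs from the documents: "Participants (N = 120) will be randomly assigned to an IPS Only (Control) or IPS Plus Abstinence-Contingent Wage Supplements group"; "Tests will be two-sided and p-values <.05 will be considered significant"; "total N required to detect differences between groups with 80% power"; "a difference of 15% between the IPS Only and the IPS Plus Abstinent-Contingent Wage Supplement with the 12 monthly assessments". For the control rate, "The adjacent figure shows possible percentages for the IPS Only group because that value affects the sample size required"; that figure is not in the readable text, and neither is the within-person correlation ρ. With exchangeable correlation,

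N = 2(1.960 + 0.842)² [p1q1 + p2q2] (1 + 11ρ) / (12 × 0.15²).

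At the worst-case rates (42.5% v 57.5%) the bracket is 0.489. ρ = 0.30 gives 122, and 120 needs ρ of about 0.29. So 120 is plausible but cannot be checked exactly. It concerns the primary outcomes, and nothing below depends on it.

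**2. Chance imbalance (assuming 60 per arm and simple allocation).** SD = √(2π(1−π)/60), where π is the prevalence at randomisation. Tail probabilities are exact binomial.

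| π | SD (points) | 10+ points apart | 15+ points apart |
|---|---|---|---|
| 50% | 9.1 | 31.5% | 12% |
| 30% or 70% | 8.4 | 27% | 9% |
| 90% | 5.5 | 9% | 1% |
| 95% | 4.0 | 2% | 0.1% |

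**3. How much carries over (injecting, no treatment effect).** Suppose that each month a share s of injectors stop and a share t of non-injectors start. With r = 1 − s − t, the average carry-over across 12 months is c = r(1 − r¹²)/[12(1 − r)]. For s = 10% and t = 3%, r = 0.87 and c = 0.87 × 0.812/1.56 = 0.453. A 10-point imbalance then moves the arm difference by 4.5 points. At π = 50%, a 95% imbalance moves it by 1.96 × 9.13 × 0.453 = 8.1 points.

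**4. Variance.** The variance of a person's 12-month rate is V = B + W. Here B = π(1−π)c². W is the average over baseline status of (1/144) Σᵢ Σⱼ pₐ(1−pₐ) r^|i−j|, where pₐ is the injecting probability in the earlier of the two months. For the case above at π = 50%, B = 0.0513 and V = 0.1432. The SE of the arm difference is √(2V/60) = 0.069 without baseline and √(2W/60) = 0.055 with it, a variance saving of 0.0513/0.1432 = 36%. A simulation of the same chain gave 0.0700 and 0.0569, or 34%.

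**5. Allowing for the urine strata already in the model.** Suppose each of the two strata copies baseline injecting with probability q and is otherwise random. Together they explain R² = 2q²/(1 + q²) of it: 0.40 at q = 0.5 and 0.66 at q = 0.7. The extra saving is (1−R²)B/(V−R²B). At q = 0.5 this is 0.6 × 0.0513/(0.1432 − 0.4 × 0.0513) = 25%. For π = 50%:

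| Stop / start per month | c | 95% shift (points) | Saving, q = 0 | q = 0.5 | q = 0.7 |
|---|---|---|---|---|---|
| 10% / 3% | 0.45 | 8.1 | 36% | 25% | 16% |
| 20% / 5% | 0.24 | 4.3 | 17% | 11% | 7% |
| 10% / 10% | 0.31 | 5.6 | 20% | 13% | 8% |
| 20% / 20% | 0.12 | 2.2 | 6% | 3% | 2% |

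The shift column ignores balance on the urines, so it is an upper figure. A simulation that balanced allocation on the strata gave 36%, 24% and 13% for the first row, 15%, 9% and 6% for the second, 6–19% for the third and 0–3% for the fourth.

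**6. Error rates in the planned kind of model.** The check used 6,000 trials per scenario; 12 monthly outcomes; independence GEE with robust SE; one urine stratifier; random-intercept SD 1; and outcome rates by baseline status of 10% v 50%, 20% v 40% or 40% v 80%.

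- All null trials: false positives 5.0–5.5% without the baseline value and 5.4–5.8% with it.
- Null trials 10+ points imbalanced: 7.8–13.4% without (15.9% at 90% prevalence) and 5.4–6.4% with.
- Null trials where the supplement arm starts 10+ points lower: median odds ratio 0.76–0.89 without and 0.99–1.00 with.
- True odds ratio of about 0.55: power 46–77% without and 72–86% with.

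**7. The other two outcomes.** For HIV risk behaviour at 10–20% baseline prevalence, a similar simulation gave a shift of 2 to 3 points and a variance saving of 11–19%, measured against a model with no covariates and so an upper figure. No estimate was made for poverty.

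**The case against.** A randomised comparison is valid without baseline values. The p-value and interval already allow for chance imbalance, and step 6 confirms an overall false positive rate near 5%. The raised rates apply only to trials picked out for being imbalanced. An aim worded as reducing a behaviour can properly mean lower than in the other arm. All of this stands. A reader might infer that the planned test is biased, or that a real reduction could never be told from a head start; the documents support neither.

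The planned model is also not unadjusted. The Background says that heroin and cocaine were chosen because they are injected, so the urine strata are partial proxies for injecting. How good they are is unknown: in step 6 a moderately correlated stratifier lowered the conditional false positive rate only from 13.4% to 11.7%. Urines do not show route of use, sharing or income.

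Low turnover fits the design poorly. The last pre-randomisation value is taken under Phase 1 abstinence pay, and the Background expects many participants to relapse once such reinforcement stops. That favours the lower rows of the step 5 table. A reader might take a saving of about a third as the expected gain; it is the top of the range.

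For poverty, everyone enters unemployed, so low income may be near-universal, and income just before randomisation includes temporary Phase 1 pay. The objection largely succeeds there.

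Finally, the section 4 schedule is introduced as serving the primary aim, and the instruments at each visit are not listed. That baseline items will be available is likely, not proven.

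**Conclusion.** The omission is real: no planned model uses pre-randomisation injecting, HIV risk behaviour or poverty. Its consequence is modest. It is an efficiency loss on secondary outcomes, plus exposure to chance imbalance in the particular trial where one occurs. At 30–70% prevalence, 10 or more points of imbalance would arise in roughly 27–32% of trials, and 15 or more in 9–12%.

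For injecting, the variance saving beyond the planned adjustment lies between near zero (20% stopping and 20% starting each month) and about a third (10% and 3%, with uninformative urine strata). It is smaller for HIV risk behaviour and probably least for poverty. All of this assumes 1:1 allocation and prevalence and turnover values that the documents do not give. The recommendation rests less on any one figure than on the fact that the change is nearly free.

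**What to change.** In 7.c, pre-specify that the following models include the outcome's own value at the last assessment before random assignment, besides the stratification covariates:

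- intervention year: injecting, HIV risk behaviour and poverty;
- follow-up year: injecting and HIV risk behaviour. Section 7.b does not list poverty among the follow-up comparisons, so no follow-up poverty model is needed.

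Add three clarifications. A missing indicator is used for anyone lacking the baseline item. The odds ratio is then conditional on baseline status, and so differs from one without that covariate even when the arms are balanced. For poverty, say whether Phase 1 pay counts in baseline income.

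An analysis restricted to baseline injectors is not needed. At 30–70% prevalence it would hold only 18–42 people per arm (0.30 × 60 to 0.70 × 60). If it is wanted, label it exploratory.

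The cost is SAP wording and one parameter per model, plus the missing indicator where used. No visit or sample size changes, provided the pre-randomisation forms are confirmed to carry these items.
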